## **8.2. Recording of Adverse Events**

At each contact with the participant, an investigator or staff member must seek information on adverse events by specific questioning and, as appropriate, by examination. Information on all adverse events should be recorded immediately in the source document, and also in the appropriate adverse event module of the case report form (CRF). All clearly related signs,

CONFIDENTIAL

symptoms, and abnormal diagnostic procedures results should be recorded in the source document, though should be grouped under one diagnosis.

All adverse events occurring during the study period must be recorded. The clinical course of each event should be followed until resolution, stabilization, or until it has been determined that the study treatment or participation is not the cause. Serious adverse events that are still ongoing at the end of the study period must be followed up to determine the final outcome. Any serious adverse event that occurs after the study period and is considered to be possibly related to the study treatment or study participation should be recorded and reported immediately.

### **8.3. Reporting of Serious Adverse Events and Unanticipated Problems**

#### **8.3.1. IRB Notification by Investigator**

A Serious Adverse Event (SAE) must be reported to the IRB within 72 hours of the event. The investigator will keep a copy of this SAE form in the study binder.

At the time of the initial report, the following information will be provided:

- Study identifier
- Study Center
- Participant number
- A description of the event
- Date of onset
- Current status
- Whether study participation was discontinued
- The reason why the event is classified as serious
- Investigator assessment of the association between the event and study participation

Significant new information on ongoing serious adverse events should be provided promptly to the IRB.

### **8.4 Unblinding Procedures**

In the event that participants are prematurely discontinued, it will be necessary to avoid breaking the blind whenever possible, in order to protect the integrity of the study. If an emergency necessitates that the blind be broken, only the pharmacist will have access to the unblinding codes and will be given the names of the staff with authority to request that the blind be broken. If the IDS or hospital pharmacy is contacted by other persons in requesting the study blind be broken for a participant, and the study physician is not reachable, the pharmacist will act according to his/her best judgment in deciding whether or not to break the study blind for that participant. The hospital pharmacist can be reached 24 hours a day by beeper to rapidly access participant unblinding codes.

***The pharmacy emergency beeper number is: [contact].***

### **8.5 Medical Monitoring**

It is the responsibility of the principal investigator at each site to oversee the safety of the study at that site. This safety monitoring will include careful assessment and appropriate reporting of adverse events as noted above. Medical monitoring will involve regular staff meetings to assess the number and type of adverse events; these meetings will be held separately at the different sites. There will be a single Data and Safety Monitoring Board for the study, which will

CONFIDENTIAL

meet twice annually to oversee safety issues for the whole study (see Section 10 Auditing, Monitoring and Inspecting).

## **8.6 Protection of Participants**

Complementing the safety measures noted above, additional procedures will be followed to protect the safety of the research participants. Potential participants will be screened for medical illnesses that would preclude the use of bupropion. Participants selected for the study will be evaluated regularly while receiving study drug treatments, both by study staff at periodic visits (as described in Table 2) and by obstetrics staff for their routine prenatal monitoring. AEs will be monitored regularly in-person or by telephone (see Table 2) and a study physician will be available at all times to evaluate and treat adverse effects of the medication. The participants' weight and blood pressure will be monitored during their standard prenatal visits and pulse rate will be measured at all in-person visits (see Table 2). AEs that reflect significant risk to the participant or fetus will result in discontinuation of the study medication, a decision that will be made by the site principal investigator together with the study obstetrician at that site. Venipuncture will be carried out with good aseptic technique by an experienced phlebotomist, nurse, or physician. Venipuncture sites will be monitored carefully for signs of infection. Participants will be given a 24-hour emergency number that they can call if necessary. The physician or nurse will clinically follow all participants who are discontinued due to a serious AE until the AE resolves and becomes completely stable, unless a referral to another physician (i.e., a specialist) is clinically indicated or requested by the participant.

## **9. Data Handling and Record Keeping**

### **9.1 Confidentiality**

Information about study participants will be kept confidential and managed according to the requirements of the Health Insurance Portability and Accountability Act of 1996 (HIPAA). Those regulations require a signed authorization informing the participant of the following:

- What protected health information (PHI) will be collected from participants in this study
- Who will have access to that information and why
- Who will use or disclose that information
- The rights of a research participant to revoke their authorization for use of their PHI.

In the event that a participant revokes authorization to collect or use PHI, the investigator, by regulation, retains the ability to use all information collected prior to the participant's revocation of authorization. For participants that have revoked authorization to collect or use PHI, attempts will be made to obtain permission to collect at least vital status (i.e. that the participant is alive) at the end of their scheduled study period.

Records, filed in the IRB office, verify that all research project personnel have completed training in the protection of human research participants in accordance with the guidelines of the U.S. Department of Health and Human Services (DHHS) and the Office for Human Research Protection (OHRP). The study staff (PI, Clinical research coordinator, etc.) will keep all study medical records (including any codes to de-identified data) under lock and key in a secure location, as required by law. Only the date and time of the research visit will be placed in the client's existing electronic medical record. All electronic data and files (e.g., database, spreadsheet, etc.) containing identifiable participant information shall be password protected. Any computer hosting such files shall have a BIOS password to prevent access by unauthorized users. If participant data are to be exchanged with others, the data will be coded. If identification is necessary, then the data will be encrypted while en route to the recipient with

CONFIDENTIAL

strong encryption levels ( $\geq 128$  bits for symmetric encryption (DES) and  $\geq 1024$  bits for asymmetric encryption (RSA). All information collected via the social media landing page will be stored securely our Data Management Unit (DMU).

All data and blood specimens will be stored without direct identifiable information, but will be identifiable via a linking code. The secured research records are labeled with code numbers only (names and other identifying information are kept separate from research records). Access to hard copy data is only given to staff members working on the study. Only staff members designated to handle or analyze study samples will have access to the samples and their storage. Coded blood samples are stored in clinic-specific refrigerators and freezers, which are located in secure rooms. As per routine in the CSA, all electronic files (e.g., database, spreadsheet) will be password protected. Any computer hosting such files will have a BIOS password to prevent access by un-authorized users.

Text messaging will be done in conjunction with Sense Health, a contractor with substantial experience in the use of text messaging in health applications. The Sense Health web service was built on top of the Amazon Web Services (AWS) cloud infrastructure, a highly secure and scalable service, that was designed in alignment with HIPAA regulations, standards, and best practices. The underlying code for the web service is version-controlled and securely backed-up on the GitHub.com. A variety of security measures have been implemented to protect PHI:

Administrative Safeguards: All Sense Health staff members are trained to understand the core requirements of HIPAA, and only authorized staff members have access to data stores that contain any PHI. Furthermore, any database containing PHI data is de-identified, so that patient information is protected even if that database is compromised.

Physical Safeguards: All of the Sense Health data and code are stored on secure cloud infrastructures such as AWS and GitHub, which were designed to comply with HIPAA regulations and best-practices.

Technical Safeguards:

*Access control:* Only authorized staff members can access the Sense Health servers on AWS and the code repository on GitHub. This access is only possible via SSH tunneling. Therefore, only authorized staff members on authorized machines can access the servers and code.

*Transmission security:* All communication between servers and the outside world is encrypted during transmission using Class 3 SSL certificates on port 443 only.

*Data encryption:* All PHI data are encrypted and stored on a MySQL AWS RDS database that is inaccessible to the outside world. This information is encrypted *before* it is stored on the database, using standard AES encryption protocols. Therefore, all patient data are de-identified before they are stored at rest.

*Data Backups:* The Sense Health databases, code, and server images are backed up both daily and hourly and stored on separate AWS availability zones, so that data are never lost and can be easily recovered when needed.

*Data Disposal:* All PHI can be permanently disposed of when no longer needed by removing those data from all active and backed-up AWS RDS databases.

CONFIDENTIAL

Blood will be collected for DNA analysis. The information derived from analysis of the participants' DNA will not be provided to the participants, since at the present time the existing preliminary genetic data for predicting response to bupropion do not provide a basis for genetic counseling. Should that situation change over the course of the study, procedures will be developed in conjunction with the UPenn and City of Philadelphia IRBs, to provide participants with relevant information on genotype and to counsel them in relation to that information. While the study is open, DNA samples will be coded with a number that provides an indirect link to the participant's identity (samples will be accessible only by the researchers and staff involved with this study). Upon completion of the study, the sample will be kept in storage indefinitely. However, the sample will forever be separated from all identifiers. These de-identified samples may be shared with other researchers and used in other projects. The lab procedures for storage include a passcode-protected locked room, and secure storage freezers. All samples will be retained securely as per lab protocols.

Data used to process subject payments with the Greenphire ClinCard program is entered electronically using secure web-based interfaces. Greenphire clinicard is HIPAA compliant. Please see document titled, "ClinCard Data Security and Privacy Statement," located in the appendix. The Greenphire system requires completing a W9 for each subject, and entering subject's name, address and social security number.

## **9.2. Source Documents**

Source data consists of all information, original records, observations, or other activities during participation in the study. Source data are contained in source documents. Examples of these original documents, and data records include: hospital records, clinical and office charts, laboratory notes, memoranda, evaluation checklists, recorded data from automated instruments, copies or transcriptions certified after verification as being accurate and complete, microfiches, photographic negatives, microfilm or magnetic media, x-rays, participant files, and records kept at the laboratories.

## **9.3. Case Report Forms**

The study case report form (CRF) is the primary data collection instrument for the study. All data requested on the CRF must be recorded. All missing data must be explained. If a space on the CRF is left blank because the procedure was not done or the question was not asked, write "N/D". If the item is not applicable to the individual case, write "N/A". All entries should be printed legibly in blue or black ink. If any entry error has been made, to correct such an error, draw a single straight line through the incorrect entry and enter the correct data above it. All such changes must be initialed and dated.

## **9.4. Records Retention**

It is the investigator's responsibility to retain study essential documents for at least 3 years after the closure of the study with the IRB.

## **9.5. Blood samples storage and retention.**

Blood for both the UPenn and Jefferson sites will be stored in a coded manner in a designated -80 degree freezer at UPenn and shipped to the laboratory of [name] at the University of Toronto, on dry ice approximately every four months or as necessary for the duration of the study. Samples will be shipped following the University of Pennsylvania's

CONFIDENTIAL

guidelines for shipping international biological samples. Samples will be coded and protected health information will not be included. DNA extraction and genotyping will be carried out in [name] laboratory. The nicotine metabolite ratio (NMR), a genetically informed biomarker based on the measurement of two long-lasting nicotine metabolites (cotinine and 3-hydroxycotinine), will also be measured. Finally, bupropion and hydroxybupropion plasma concentrations will be measured using blood obtained at the week-5 visit.

## **10. Study Monitoring, Auditing, and Inspecting**

### **10.1. Study Data and Safety Monitoring Plan**

This study will be monitored according to the attached Data and Safety Monitoring Plan (DSMP) version 1, dated 7/6/2016 (see Appendix). The DSMP includes 100% source data verification to be performed for each subject, at each site, to ensure that all of the essential aspects of the Sponsor's oversight of the research at all sites are addressed. The Principal Investigator will identify an appropriately trained staff member and allocate adequate time and supervision for such monitoring activities to occur. The Investigator will also ensure that the monitor is given access to all of the study-related documents and, has adequate space to conduct the monitoring visit.

## **SAFETY MONITORING AND REPORTING PROTOCOL**

**Adverse Event Determination and Reporting Procedures.** For this study, we will use established Penn procedures and infrastructure for data and safety monitoring and a protocol-specific Data and Safety Monitoring Board (DSMB). The specific elements of our plan is as follows: 1) all project staff will complete certification in the protection of research participants; 2) the protocol will be submitted for review to the IRB and all procedures and policies outlined by the IRB will be followed for this study; and 3) a DSMB will be established to review the progress of accrual and the safety of participants. We will supply the designated IRB with ongoing progress reports for the study and a formal review of the study will be conducted annually or more frequently as designated by the IRB. The Penn IRB will act as the IRB of record for both sites per the IRB Authorization Agreement signed by both sites. The City of Philadelphia IRB will receive an annual report and be informed of all SAEs and reportable events. The IRB may suspend, terminate or restrict the study as appropriate. Each participating investigator must complete certification in the protection of research participants. Finally, [name] (at Penn) and [name] (MATER/Jefferson) will manage the flow of documents to external agencies to facilitate ongoing and timely review. The IRB will audit the study as needed and will review all data on a regular basis at least every 12 months. All serious adverse events (SAEs) will be reviewed on a real-time basis first by the study physicians. An existing protocol for adverse event monitoring and adverse event reporting will be used (see below). The DSMB will consist of four individuals who are not involved in the study: a statistician ([name]., Assistant Professor of Medical Science at Quinnipiac University), an obstetrician ([name]., Associate Professor of Obstetrics and Gynecology at Penn), a clinical trialist ([name]., Professor of Psychiatry at Penn) and a women's behavioral wellness specialist ([name], Professor of Psychiatry and Ob/Gyn at Penn). The DSMB will establish guidelines for adverse event reporting. The DSMB will meet annually, with additional meetings, as may be required. Prior to meetings, all members of the DSMB will receive a report describing study progress, including enrollment, treatment completion or early termination, and a summary of all adverse events. A formal data and safety monitoring plan, detailing the DSMB's activities, will be submitted to the IRB for review and approval prior to study initiation and periodic reports will be included with annual IRB reviews.

## **PARTICIPANT SAFETY MONITORING PROTOCOL**

**Monitoring Participant Safety.** For this trial, we will use a method to track, manage, and report adverse events that was used in completed studies (14, 43, 52) and is being used in an ongoing (U01 DA020830) pharmacotherapy trial. First, in terms of personnel, each clinical site will include a study physician, a study psychologist, and a research nurse/qualified medical staff person to handle comprehensive eligibility screening, monitoring of participant reactions and adverse events, and the management of any adverse events. The initial eligibility screening procedures will involve careful assessment of participants' medical history to ensure that individuals with pre-existing conditions that can increase adverse event risk are excluded. Second, we will use a two-tiered system to assess potential adverse events. Site staff will complete a baseline adverse event checklist (week 0). At weeks 1, 3, 5, 7, and 10, staff members will conduct an open-ended evaluation of any potential adverse event and complete the established checklist of adverse events. Lastly, as done in our previous clinical trials, participants will be provided with contact information (a wallet-size card) so that, if a serious adverse event occurs, they have methods to contact study staff at their respective clinical site 24 hours a day. Because participants may try to communicate regarding adverse events through the daily text messaging service, which will not be monitored for this purpose, we will provide contact information via an auto-message informing the participant of how to reach study staff in an emergency.

For all adverse events, the site nurse practitioner, in consultation with the site PI and the obstetrician at each site (as needed), will determine a course of action (i.e., continuation and monitoring, dose reduction, participant withdrawal). All adverse events that are considered Serious Adverse Events (see below) will be reported to site PIs and IRBs at all clinical sites, as well as to the FDA and NIH (see below for protocol for adverse event reporting). Site PIs and study physicians will determine whether a serious adverse event requires additional care. Such events may be referred to the outpatient department at the clinical site or to the emergency department of the clinical site (all sites have access to 24-hour emergency services, including extensive inpatient and outpatient services for psychiatric conditions).

### **MEASURES FOR PARTICIPANT SAFETY.**

**Medication Adverse Events Checklist.** An adverse events checklist will assess the frequency and severity of common adverse events associated with bupropion (rated as: none, mild, moderate, or severe). This measure will be conducted at weeks 1, 3, 5, 7, and 10. This assessment is meant to monitor participant safety and reduce or stop treatment if need be. But, adverse events will be considered an outcome and a covariate in the analysis, as the overall frequency and/or as the presence (ever) of specific common adverse events. Our adverse events measure includes items that have been reported from bupropion use. In addition, we will monitor the prenatal care record to identify adverse obstetrical events, which will be recorded and reviewed regularly by the study team at each site. The data will be fully abstracted at the time of delivery for use in data analysis, which will provide a second opportunity to review obstetrical adverse events that may have occurred during the pregnancy.

**Open-ended Questions.** In addition, open-ended questions concerning adverse events are assessed at these weeks. Staff will probe for physical and psychiatric adverse events. This method is included to supplement standard adverse event measures so non expected adverse events will be captured. Events will be classified as none, mild, moderate, or severe.

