#### Mediators and Moderators of Bupropion Response

##### **Depressive Symptoms and Craving as Mediators of Bupropion's Therapeutic Effects:**

Pregnant smokers who are depressed are less likely to quit smoking than those who are not (28). In pregnant minority women, even mild depression nearly doubled the risk of continued smoking (56). Thus, we expect that, given bupropion's well-established antidepressant effects (57, 58), its efficacy as a treatment for ND will be mediated by reductions in depressive symptoms. Likewise, several symptoms that are present in pregnant smokers before quitting smoking (e.g., irritability, anxiety, difficulty concentrating, insomnia, restlessness, increased appetite, depressed mood, drowsiness) are similar to those that occur commonly during nicotine withdrawal (59). Compounded by nicotine withdrawal, these symptoms may make it more difficult for pregnant women to quit smoking (34). Because bupropion mitigates craving associated with nicotine abstinence, we expect that its efficacy in treating ND in pregnant women will also be mediated by a reduction in craving.

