### **Potential Risks**

The most common adverse events associated with bupropion when used for smoking cessation are dry mouth (11%), insomnia (31%) and dizziness (8%).

Frequent adverse reactions (occurring in at least 1% of patients) include rhinitis, neck pain, allergic reaction, hot flashes, hypertension, increased appetite, anorexia, constipation, arthralgia, myalgia, tremor, somnolence, thinking abnormality, bronchitis, pruritis, rash, dry skin, urticaria, taste perversion, asthenia, fever, headache, dyspepsia, vomiting, agitation, depression, irritability sweating, blurred vision or diplopia, and urinary frequency (Zyban Package Insert).

Infrequent adverse reactions (occurring in less than 1% but greater than 0.1% of patients) include: chills, inguinal hernia, photosensitivity, flushing, migraine, postural hypotension, stroke, tachycardia, vasodilation, abnormal liver function, bruxism, dysphagia, gastric reflux, gingivitis, jaundice, stomatitis, ecchymosis, edema and peripheral edema, leg cramps and twitching, abnormal coordination, CNS stimulation, confusion, decreased libido, decreased memory, depersonalization, emotional lability, hostility, hyperkinesia, parkinsonism, hypertonia, hypesthesia, paresthesia, suicidal ideation, and vertigo, accommodation abnormality and dry eye, polyuria, and urinary urgency (Zyban Package Insert).

Rare adverse reactions (occurring in less than 0.1% of patients) include: malaise, syncope, amnesia, ataxia, derealization, hypomania, and bronchospasm (Zyban Package Insert).

Bupropion is contraindicated in patients with a history of seizure disorder or in patients with a current or prior diagnosis of bulimia or anorexia, because of a higher incidence of seizures in these individuals when treated with bupropion.

Patients taking bupropion for smoking cessation have experienced mood changes, including depression or mania, psychosis, hallucinations, paranoia, delusions, homicidal ideation, hostility, agitation, aggression, anxiety, and panic, as well as suicidal ideation, suicide attempt, and completed suicide.

Abuse potential: Bupropion is not likely to be reinforcing to users of stimulants, including amphetamines. Abuse of bupropion by inhalation or injection of crushed tablets have been reported, resulting in seizures and/or death.

The risk of bupropion for smoking cessation in pregnant women has not been adequately evaluated. There is a risk that bupropion could adversely affect the developing fetus.

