## **7.2. Statistical Analyses**

[name] will oversee analyses, which will be conducted using Stata, SAS, or R-Language software. Preliminary analyses will assess sample characteristics (e.g., dependence, race) by treatment using t-test or contingency table methods. These variables will also be examined for their relationship to completion of outcome assessments. Variables related to treatment arm or completion of follow ups will be included as covariates in analyses of study aims. Compliance measures will be evaluated across treatment arms, and controlled for in primary analyses. We will examine the correlation between self-report and pill count data and week-5 bupropion plasma levels. We will use intent-to-treat as the primary method to evaluate study aims.

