### **7.2.2. Specific Aim 1: To compare the efficacy of bupropion with placebo for smoking cessation in pregnant smokers.**

For **H1**, we will test for treatment group differences in a binary abstinence outcome that is a repeated measure using a generalized estimating equations (GEE) model with a logit link. Quit rates at the end of week 10 of treatment and 24 weeks post-TQD will represent our primary outcome variables. Medication group (bupropion vs. placebo) and time point (end of week 10 of treatment and 24 weeks post-TQD) will be treated as categorical predictor variables, and the model will predict separate effects of treatment on abstinence at each time point (an interaction). Our initial analyses will be stratified by site, and we will carefully examine the models for differences by site, testing for an overall interaction. We will use baseline depression (PHQ-9 score of 10) to stratify the randomization. The model may include a small number of covariates added to control error or adjust for confounding [e.g., age, history of pre-term delivery, baseline gestational age, daily smoking rate]. Any variables found to be associated with both outcome and treatment assignment will be entered as covariates. In the absence of an overall interaction (by site), we will pool the study population and account for site in the model as a binary predictor. To evaluate the effectiveness of randomization, we will compare summary statistics for participant characteristics in the two study arms. If there is an imbalance in participant characteristics, statistical adjustment will be used to ensure that the initial results were not biased by it.

Because many participants will fail to become completely abstinent, but may show a reduction in smoking, we will examine cigarette consumption as a secondary outcome. The analysis will be similar to the primary analysis, except that we examine the effect of treatment arm on daily cigarette counts using a GEE model with a negative-binomial link. Likewise, time to (recurrent) event models will be fitted using Cox regression, stratified by event sequence, as in Schnoll et al. (52), to assess lapse and recovery events over 24 weeks.

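### Section 10.1 makes on-treatment adverse events a covariate without naming the model, and Section 7.2 does not keep them out of the abstinence analysis

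*Combined protocol and SAP*

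**What the plan says.** **Section 10.1, Measures for Participant Safety (Medication Adverse Events Checklist).** The plan states that "adverse events will be considered an outcome and a covariate in the analysis", in the form of AEs "as the overall frequency and/or as the presence (ever) of specific common adverse events". On timing: "This measure will be conducted at weeks 1, 3, 5, 7, and 10". All five occasions follow randomisation. A separate baseline checklist is completed before the first dose (Sections 6.3 and 10.1), but it is not the measure given the covariate role.

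**Section 7.2.2, abstinence model (H1).** "The model may include a small number of covariates added to control error or adjust for confounding". The examples are all baseline variables: age, earlier preterm delivery, gestational age at entry and smoking rate. AEs are not among them. The section then adds: "Any variables found to be associated with both outcome and treatment assignment will be entered as covariates". That rule is not limited to variables measured before randomisation.

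**Section 7.2.2, H2.** Here AEs are the outcome, in the equivalence analysis.

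**Section 7.2.** A different post-randomisation variable is placed explicitly in the main models: "Compliance measures will be evaluated across treatment arms, and controlled for in primary analyses".

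**Background.** Section 1.5 lists insomnia (31%), dry mouth (11%) and dizziness (8%) as the commonest AEs of bupropion in smoking cessation. Section 1.1 says that symptoms including irritability, anxiety, insomnia and low mood "are similar to those that occur commonly during nicotine withdrawal". Irritability, anxiety, insomnia and depressed mood are also items on the AE checklist.

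**The concern.** Because H2 already uses AEs as the outcome, their covariate role must fall on some other model, and the abstinence model is the obvious candidate. Nothing in Section 7.2 excludes it, and nothing confines AE adjustment to a sensitivity or exploratory analysis. An analyst could put an on-treatment AE into the primary GEE and fairly say that the protocol allowed it.

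The documents make both relevant links plausible. The drug is associated with some checklist symptoms, and quitting may change the reporting of others through withdrawal. Where one AE carries both links, comparing arms within levels of that AE no longer compares randomised groups. Section 3.2 also says that AEs can lead to dose reduction or suspension, so they may lie on the path from assignment to outcome.

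At stake is whether the primary odds ratio is the randomised effect, and whether its value depends on which AE is chosen. Section 10.1 leaves that choice open.

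**Working it through.** **1. The plan's own power figure.** Section 7.1.1 gives 21.2% on placebo, 35.9% on bupropion, N = 360 and 88% power. Section 5.3 gives 180 per arm, and Section 7.1 gives two-sided α = 0.05.

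- Odds ratio: (0.359/0.641) / (0.212/0.788) = 2.08; log OR = 0.733.
- Pooled z: null SE = √(2 × 0.2855 × 0.7145/180) = 0.0476; alternative SE = √[(0.212 × 0.788 + 0.359 × 0.641)/180] = 0.0470. Power = Φ[(0.147 − 1.96 × 0.0476)/0.0470] = 87.3%.
- Unpooled z: Φ(0.147/0.0470 − 1.96) = 87.9%.
- Logistic Wald test: SE = √[1/(180 × 0.212 × 0.788) + 1/(180 × 0.359 × 0.641)] = 0.240; power = Φ(0.733/0.240 − 1.96) = 86.4%.

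The stated 88% is reproduced, and it contains no AE adjustment. The Wald figure of 86% is the reference below, because the adjusted model is logistic.

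**2. Adding an AE term.** Expected counts were formed for arm × abstinence × AE at 180 per arm, and abstinence was regressed on arm and AE. Inputs:

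- Any moderate-to-severe AE: 55% on bupropion and 53% on placebo, the complements of the 45% and 47% without one in Section 7.1.1.
- Insomnia: 31% on bupropion (Section 1.5). The documents give no placebo rate; 15% and 21% are assumed.
- Odds ratio between the AE and quitting within arm: not in the documents; 1/3 to 3 is assumed.

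**3. One case in full: insomnia 15% vs 31%, AE-quitting OR 3.** Solving for the marginal rates gives AE risks of 11.5% (non-quitters) and 28.0% (quitters) on placebo, and 22.4% and 46.4% on bupropion. Among women without the AE:

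OR = 2.08 × [(1 − 0.464)/(1 − 0.224)] / [(1 − 0.280)/(1 − 0.115)] = 2.08 × 0.691/0.813 = 1.77.

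The stratum with the AE gives the same value. The adjusted log OR is 0.570 with SE 0.248, so power = Φ(0.570/0.248 − 1.96) = 63%.

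**4. Results.** In the null columns both arms quit at 21.2%.

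| AE in the model (placebo vs bupropion) | AE-quitting OR | Adjusted OR | Power | Null OR | Null rejection |
|---|---|---|---|---|---|
| None | – | 2.08 | 86% | 1.00 | 5.0% |
| Any moderate-to-severe, 53% vs 55% | 1/3 | 2.23 | 90% | 1.02 | 5.1% |
| Same | 3 | 2.12 | 86% | 0.98 | 5.1% |
| Insomnia, 21% vs 31% | 1/3 | 2.35 | 94% | 1.10 | 6.4% |
| Same | 3 | 1.92 | 75% | 0.88 | 7.7% |
| Insomnia, 15% vs 31% | 1/3 | 2.48 | 96% | 1.16 | 8.5% |
| Same | 3 | 1.77 | 63% | 0.81 | 11.9% |

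With both arms at the pooled rate of 28.55% instead, the lowest null OR is 0.82.

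**5. Reading the table.** Part of any shift in an odds ratio when a covariate is added is non-collapsibility, which is not bias. The null columns separate the two. For overall AEs the null OR stays at 0.98 to 1.02 and the rejection rate at about 5%. For insomnia the null OR departs from 1 and the test rejects too often. The 94-96% power figures are not a gain, because they come from an inflated estimate.

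**6. Both links are needed.** If the AE depends only on the drug (AE-quitting OR 1), or only on quitting with no direct drug effect, the adjusted OR stays at 2.08.

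**The case against.** The best defence is that Section 10.1 names no model. The sentence sits in a safety-monitoring paragraph, whereas the section that specifies the abstinence model makes covariates optional and gives only baseline examples. A reader might infer that the plan requires AEs in the primary model. The documents do not say so. They leave the matter open, and the rule on variables tied to both arm and outcome is the route by which AEs could enter.

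The second defence is size. The protocol's only AE rates by arm for bupropion differ by 2 points. With quitters reporting 15 to 20 points more AEs, or 15 points fewer, the adjusted OR is 2.08 to 2.14 and power is 86-88%. This stands for overall AE occurrence, which is close to one of the two forms that Section 10.1 allows. It does not answer the other form, specific AEs.

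Third, the causal links are weaker than they may look. Section 1.1 describes the overlapping symptoms as present before quitting, which may narrow the gap between quitters and non-quitters. It also expects bupropion to ease depressive symptoms, so the drug need not raise every item. Dry mouth is not among the withdrawal symptoms listed. For the week-24 outcome, AEs recorded to week 10 come first and are intermediates rather than consequences. All of this stands. It makes the bias conditional and its direction unknown, but it does not make the adjustment safe.

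A reader might also infer that the damage could not be undone. That is not so: the data are unaffected, and refitting without the AE term restores the randomised estimate.

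**Conclusion.** The point holds as a gap in specification that should be closed. The plan gives on-treatment AEs a covariate role, does not say where, and has a selection rule in Section 7.2.2 that could bring them into the abstinence model. Such an adjustment would replace the randomised effect with a different quantity.

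The size depends on which AE is used. For overall moderate-to-severe AEs at 55% vs 53% the bias is negligible. For insomnia at 31% vs an assumed 15-21%, with an assumed AE-quitting OR between 1/3 and 3, the adjusted OR lies between 1.77 and 2.48 against 2.08. Power lies between 63% and 96% against 86%, the null OR is about 0.81 to 1.16, and the false-positive rate reaches 11.9%. Those ranges rest on the assumed placebo rate and AE-quitting association.

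The documents do not support the stronger statement that the planned abstinence estimate *is* biased, or biased in a known direction. Birth weight and the mediation models were not quantified.

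**What to change.** 1. In the checklist paragraph of Section 10.1, delete the words *and a covariate*.
2. In Section 7.2, state that the primary efficacy models adjust only for variables measured before randomisation, and restrict the Section 7.2.2 rule on variables associated with arm and outcome in the same way. The baseline AE checklist would remain eligible.
3. Label any analysis of abstinence by on-treatment AEs as exploratory.

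The sentence in Section 7.2 that controls for compliance in primary analyses would contradict item 2, so it must be changed at the same time.

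The cost is a few words of text, settled before unblinding. Sample size, data collection and safety monitoring do not change. At the planned rates the estimate remains the randomised OR of 2.08, with the power of about 87-88% that the plan intended.
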